6.2.3. FIX:C

6.2.3.1. Main Analysis

A log transformation of the steady state FIX:C (as the endpoint defined in Section 3, the geometric mean is the antilog of the mean of the log-transformed values) will be compared to a threshold of log(5) using a one-sided, one-sample t-test.

- The Dosed population will be the primary analysis population. Analysis will also be done on the Evaluable population if it is different from Dosed population.
- The sample size, mean and t-based 95% CI, standard deviation, median, Q1, Q3, minimum, and maximum of FIX:C (all descriptive statistics will be transformed back to original scale) will be presented in the summary tables. For the primary analysis,

assessments with missing data imputation will be utilized. Another supportive analysis will also be conducted with only observed data.

6.2.3.2. Sensitivity/Supplementary Analyses

Similar analyses comparing the FIX:C Year 2 to 6 to the threshold of 5% will be conducted. The window for Year 2 will be from Month 15 through Month 24 as previously described. The above analysis will be conducted on Dosed population.

Similar summaries will also be provided for FIX:C during the following periods: prior to corticosteroid initiation, during corticosteroid treatment and post-corticosteroid treatment (Section 5.2) for the participants in whom corticosteroid is initiated. FIX:C during the overall time period (Week 12 to Month 15) for participants who do not have corticosteroid treatment will be presented side by side in the same table.

An individual plot will be generated to visualize FIX:C values of the Dosed population. The graph will display all FIX:C measurements excluding the ones within the window of FIX infusion.

Actual value of FIX:C will be presented in a summary table by study visit with mean, SD, 95% CI of the mean, median, min, max, Q1 and Q3. A box-whisker plot will also be provided for data visualization purpose. In addition, a stacked bar graph will be generated by study visit, presenting percentage of participants falling into the following category (FIX:C: 0-<5%, 5-<15%, 15-<50%, 50-<150%, $\geq 150\%$). If a participant withdrew consent, dropped out early from the study or resumed FIX prophylaxis, then the missing assessment will be imputed as 1.9%. For the primary analysis, assessments with missing data imputation will be utilized for summaries. Another supportive analysis will also be conducted with only observed data.

The FIX:C results by two different one-stage assays along with analysis by chromogenic assay will be visualized in graphs with chromogenic value on the x-axis and both one-stage assay results on the y-axis. The FIX:C results of two-stage assays will be visualized using scatter plot.

The Pearson's correlation will be calculated for each pair of the three assays.

6.2.4. Annualized FIX Consumption

This endpoint will be analyzed similarly as AIR, including alternative endpoint definitions, main analysis, sensitivity analysis, timing of the analysis, and table presentation.

6.2.5. Annualized Bleeding Rate of Specific Type

The ABR_{total} of specific types such as spontaneous bleeding, traumatic bleeding, bleeding in joints, bleeding in soft tissue, and untreated bleeding etc. These endpoints will be analyzed similarly as defined for main analysis of ABR_{total}.

These analyses will be conducted on Dosed population.

6.2.6. Percentage of Participants without Bleeding

Percentage of the participants without treated bleeding will be defined in the overall time period after PF-06838435 infusion, the running total time period (i.e., Week 12- Month 15, Week 12-Year 2, Week 12- Year 3, etc.) and with the same time periods as ABR such as Week 12 to Month 15, Year 2 (Month 15 to Month 24), Year 3, Year 4, Year 5 and Year 6.

The percentage of participants without any bleeding (including treated and untreated) will be defined as well in the overall time period after PF-06838435 infusion, the running total time period (i.e., Week 12- Month 15, Week 12-Year 2, Week 12- Year 3, etc.) and with the same time periods as ABR such as Week 12 to Month 15, Year 2 (Month 15 to Month 24), Year 3, Year 4, Year 5 and Year 6.

Descriptive statistics will include the number of participants, frequencies, and the percentage of participants who have/have no bleeding. The Dosed population will be used for this analysis.

6.2.7. Hemophilia Joint Health Score (HJHS)

The HJHS total score at different time points will be compared to its baseline using paired t-test.

The n, median, mean and standard deviation, the 95% confidence limits of actual value and the change from baseline will be reported in the summary table. The Dosed population will be used for this analysis.

The HJHS value at different visits will be analyzed in a longitudinal model as exploratory analysis to study the trend of the HJHS using MMRM model with participant as random factor, and years since infusion as the continuous variable. The Dosed population will be used for this analysis.

6.2.8. Patient-Reported Outcomes

Patient Global Impression of Change – Hemophilia (PGIC-H) will enable an anchor-based method approach for evaluating the meaningful within-patient change (MW-PC) for Haem-A-QoL, HAL and HLIQ (described in Section 6.3.2). The details about anchor analysis will be provided in a separate PRO SAP and thus not described in detail here.

6.2.8.1. Haem-A-QoL

The 10 domains of health-related quality of life as well as the total score will be calculated, and each compared to its own baseline using paired t-test. The Physical Health domain will be the main endpoint of this instrument. The n, median, mean and standard deviation, the 95% confidence limits of actual value and the change from baseline will be summarized by visit in the table. The Dosed population will be used for this analysis.

6.2.8.2. Hemophilia Activities List (HAL, v2)

The 7 domains of the HAL and three component scores can be calculated and will each be compared to its own baseline using paired t-test. Complex activities involving the Lower Extremities will be main endpoint for this instrument. The n, median, Q1, Q3, minimum, maximum, mean and standard deviation, the 95% confidence limits of actual value and the change from baseline will be reported by visit in the summary table. The Dosed population will be used for this analysis.

6.2.9. Immunogenicity

Percentage of participants with positive/negative IFNy to each pool, FIX overall and capsid overall will be summarized by the specified sampling timepoint for participants in whom the corticosteroid treatment is initiated.

Descriptive summaries will be provided for nAb to AAV titer by study week. Number and percentage of participants with positive nAb to AAV will also be summarized by study week. Unscheduled assessments will also be presented. Data will also be presented in a listing.

Descriptive summaries will be provided for ADA by study week. Number and percentage of participants with positive ADA will also be summarized by study week. Unscheduled assessments will also be presented. Data will also be presented in a listing. Two scatter plots will be generated, plotting steady state FIX:C against ADA titer at Screening visit and ADA titer at Week 52, respectively.

Number and percentage of participants with FIX inhibitor by the Bethesda Assay post PF-06838435 infusion will be summarized.

6.3. Other Endpoint(s)

6.3.1. Joint Assessments

6.3.1.1. Target Joints

Number and percentage of participants with 0, 1, 2 or \geq 3 target joints at baseline, during the first 15 months post PF-06838435 infusion, and during the overall follow-up period will be summarized, respectively. Number and percentage of participants who have 0, 1, 2 or \geq 3 baseline target joints resolved during the first 15 months post PF-06838435 infusion, and during the overall follow-up period will be summarized. Similarly, number and percentage of participants who developed new target joints (1, 2 or \geq 3 target joints) during the first 15 months post PF-06838435 infusion, and during the overall follow-up period will be summarized. Similarly, number and percentage of participants who developed new target joints (1, 2 or \geq 3 target joints) during the first 15 months post PF-06838435 infusion, and during the overall follow-up period will be summarized. The number and location of target joints at baseline and post PF-06838435 infusion will be provided in a data listing.

The Dosed population will be used for this analysis.

6.3.1.2. X-ray Assessments to Evaluate Joints

The overall score, the score at specific joint, and target joint, as well as the change from baseline will be summarized by study visit. The assessment values will be compared to baseline using paired t-test. The summary table will include two columns, for FIX prophylaxis and PF-06838435, respectively. The n, median, Q1, Q3, minimum, maximum, mean and standard deviation, the 95% confidence limits of actual value and the change from baseline will be reported in the summary table. The "X-ray substudy" population will be used for this analysis.

6.3.1.3. Magnetic Resonance Imaging (MRI) to Evaluate Joints

Final score combining soft-tissue and osteochondral sub-scores would be assessed to form a total score of joint image from 0-5 (0 to be the best and 5 to be the worst) will be compared to baseline using paired t-test. The summary table will include two columns, for FIX prophylaxis and PF-06838435, respectively. The n, median, Q1, Q3, minimum, maximum, mean and standard deviation, the 95% confidence limits of the actual value and the change from baseline will be reported in the summary table. The 'MRI substudy' population will be used for this analysis.

6.3.2. Additional Patient-Reported Outcomes

All PRO endpoints will be analyzed as continuous variables, each patient's post PF-06838435 infusion value will be compared to its own baseline using paired t-test to test whether the difference from baseline is greater than '0'. PGIC-H will enable an anchorbased methodology approach for evaluating the MW-PC. The details about anchor analysis will be provided in a separate PRO SAP and thus not described here.

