3.2.8.1. Haemophilia Quality of Life Questionnaire for Adults (Haem-A-QoL)

The Haem-A-QoL Questionnaire is designed for adult (\geq 17 years) patients with hemophilia. It contains 46 items with ten domains that assess health in the following areas: Physical Health (5 items); Feelings (4 items); View of Self (5 items); Sports and Leisure (5 items); Work and School (4 items); Dealing with Haemophilia (3 items); Treatment (8 items); Future (5 items); Family Planning (4 items); and Partnership and Sexuality (3 items). The total score is also considered.

Each item has a response on the 5-point Likert Scale ranging from "Never" to "All of the time" with several items having a "not applicable" option.

The items prompt the responder to consider life in the last four weeks ("four-week recall"). The items are self-explanatory and the questionnaire can be completed in about 15 minutes.

Scoring is performed by averaging the non-missing item responses for each domain, and then rescaled to be on 0 to 100, with lower scores representing higher quality of life. The total score is directly averaged across the 46 items values and then rescaled on zero to 100.

A domain score can be calculated if \geq 50% of that domain's items have been answered.

There is an expectation that the questionnaire is being administered electronically and designed such that patients are not able to skip items. That is, there should not be any missing items unless the participant does not complete the questionnaire.

The Physical Health domain is considered as the primary domain in this questionnaire and is a secondary endpoint, and will be further assessed using the anchor-based method for each yearly visit.

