3.2.8.2. Hemophilia Activities List (HAL, v2)

The Hemophilia Activities List (version 2) is a multiple domain measure of the impact of hemophilia on functional abilities in adults. The 7 domains of this instrument contain 42 items in total, as follows: Lying/sitting/kneeling/standing (8); Lower (leg) functioning (9); Upper (arm) functioning (4); Transportation (3); Self-care (5); Household tasks (6); and Sports/Leisure (7). An overall sum score and three component scores can be calculated along with individual domain scores.

All individual items are rated on a 6-point scale from 1 (impossible) to 6 (never) describing difficulty due to hemophilia in the past month. Several items allow the respondent to mark as "not applicable."

Selected items from five of the domains are used to create three components: upper extremity; basic lower extremity; and complex lower extremity activities.

Responses from individual items can be summed to give a score for each domain and component, and the total. Higher values indicate better quality of life, that is, higher values indicate less functional limitations in performing tasks.

The activities list also includes two sets of multiple-choice items assessing the use of adaptive and assistive devices; these items are not included in the scoring.

Each domain or component, or the total, must have a minimum number of valid responses or the score is set to missing. An implication of the "minimum number of valid responses" is that there is an acceptable amount of missing data where the scores (domains, components, and total; score and normalized score) can still be calculated.

The component score of "complex lower extremity activities" is considered the most important in this questionnaire and is a secondary endpoint, and will be assessed using the anchor-based method for each yearly visit. Hemophilia Activities List baseline is the closest evaluation prior to or on the day of PF-06838435 infusion, which is measured during the screening period of Study C0371002. The normalization method to derive score of domains and three components will be used to impute any missing item.

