3.3.2. Additional PRO Assessments

3.3.2.1. Hemophilia Life Impacts Questionnaire (HLIQ)

The Hemophilia Life Impacts Questionnaire (HLIQ) is a 9-item assessment of life impacts associated with living with and treating hemophilia. The HLIQ employs a 'past week' recall period. Four items are assessed on a 5-point, ordinal, verbal rating scale (VRS) scored from 0 to 4, while 4 items are rated such that responding 'yes' branches to a 5-point, ordinal VRS and responding 'no' branches to a reason for not participating in the activity, i.e., due to hemophilia or due to other reasons. One item is assessed on a 4-point, ordinal VRS scored from 0 to 3. Higher scores on the VRS indicate greater impact due to living with or treating hemophilia. HLIQ baseline is the closest evaluation prior to or on the day of PF-06838435 infusion, which is measured during the screening period of Study C0371002.

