5.1. Hypotheses and Decision Rules

In this study, all hypothesis testing will use a two-sided test, unless specified otherwise.

The primary objective is to demonstrate the efficacy of a single infusion of PF-06838435 in male participants \geq 18 years of age with moderately severe to severe hemophilia B (FIX:C \leq 2%). The primary objective is addressed via the primary endpoint of ABR_{total}.

The hypothesis test of ABR_{total} is noninferiority test of pre- and post treatment with PF-06838435 with a noninferiority margin of 3.

A gatekeeping process will be applied to control multiplicity of testing multiple endpoints at the primary analysis. The subsequent hypothesis testing will only be performed after success on a previous hypothesis test, each test performed at the α defined for the primary analysis (0.05). The analyses cease when a failure occurs. The sequence of gatekeeping process is displayed in Table 2. For the last group of hypothesis tests, we would apply Hochberg (1988) step-up procedure so that the familywise error rate will be controlled under 0.05. Note, only selected endpoints are included in the sequence in the table below.

			Hypothes	is testing ce	eases when	a failure occ	ours		
ABR _{total} non- inferior to FIX prophyla xis regimen#	ABR _{treat} non- inferior to FIX prophylaxis regimen#	AIR superior ity to FIX prophyl axis regimen	Steady state FIX:C >5%*	FIX consump- tion superiority to FIX prophylaxi s regimen	ABR _{treat} superiority to FIX prophylaxi s regimen	ABR _{total} superiority to FIX prophylaxi s regimen	Haem-A- QoL Physical Health domain significantly improved from baseline	HAL Complex Lower extremity Activities compone nt score signifi- cantly improved from baseline	ABR _{total} of specific type (spontaneous , trauma, untreated, in target joints,) non-inferior to FIX prophylaxis regimen, and HJHS (Hochberg step-up method)

Table 2. Sequence of Gatekeeping Process of Multiple Hypothesis Tests

#The upper bound of the confidence interval of the difference in ABR_{total} and ABR_{treat} between pre- and post PF-06838435 will be compared to the NI margin. All other hypothesis tests are 2-sided tests. *Steady state FIX:C will be analyzed using a one-sided, one sample t-test.

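### SAP 6.3.2 gives all patient-reported outcomes one direction of test, which is worsening on Haem-A-QoL and conflicts with the two-sided rule in SAP 5.1

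*SAP*

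**What the plan says.** SAP 6.3.2 (Additional Patient-Reported Outcomes, under Other Endpoints) opens with a rule for all PRO endpoints. Each is treated as continuous, and the post-infusion value is set against the participant's own baseline by a "paired t-test to test whether the difference from baseline is greater than" zero. The order of subtraction is not defined.

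The instruments do not share a direction:

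- Haem-A-QoL (SAP 3.2.8.1): domain scores run from 0 to 100, "with lower scores representing higher quality of life".
- HAL (SAP 3.2.8.2): "Higher values indicate better quality of life".
- HLIQ (SAP 3.3.2.1): "Higher scores on the VRS indicate greater impact due to living with or treating hemophilia".

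Sidedness is set in SAP 5.1: "In this study, all hypothesis testing will use a two-sided test, unless specified otherwise". The Table 2 footnote first covers the two non-inferiority comparisons, then adds "All other hypothesis tests are 2-sided tests", and marks one exception: "Steady state FIX:C will be analyzed using a one-sided, one sample t-test". Step 8 of the ten in Table 2 is the Haem-A-QoL "Physical Health domain significantly improved from baseline"; step 9 is the HAL complex lower extremity component, with the same criterion. Each test is at 0.05, and testing stops at the first failure.

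SAP 6.2.8.1 and 6.2.8.2, the sections for Haem-A-QoL and HAL, specify a paired t-test against baseline and give no direction.

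**The concern.** One directional rule has been written for instruments that score in opposite directions. With post minus baseline, a positive difference is improvement on HAL but deterioration on Haem-A-QoL. With baseline minus post, the problem moves to HAL. The sentence cannot be right for both.

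The rule also reads as one-directional, although SAP 5.1 makes tests two-sided. That default yields where something else is specified, and a programmer could take 6.3.2 as such a specification. A real gain on a Haem-A-QoL score would then be reported as non-significant, and a real loss could be reported as significant. If the same code were used for the Physical Health domain, step 8 would fail and formal testing would end before HAL (step 9) and the final Hochberg group of bleed types and HJHS (step 10).

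**Working it through.** The documents give no effect size, standard deviation or power for any PRO, so there is no planned figure to reproduce. The check has two parts: the passages compared, then an illustration of what the literal sentence would do.

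**Passages compared**

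| Instrument | Improving sign, post minus baseline | Does a difference above zero mean improvement? | How it is analysed |
|---|---|---|---|
| Haem-A-QoL | negative | no | paired t-test (6.2.8.1); Physical Health is step 8 |
| HAL | positive | yes | paired t-test (6.2.8.2); complex lower extremity component is step 9 |
| EQ-5D-5L VAS | positive (0 worst, 100 best) | yes | paired t-test (6.3.2.3); not in Table 2 |
| EQ-5D-5L index | not stated | cannot be said from the documents | paired t-test (6.3.2.3); not in Table 2 |
| HLIQ | negative | no | counts and percentages only (6.3.2.2); not in Table 2 |
| PGIC-H | not a change score | not applicable | categorical summary (6.3.2.1); not in Table 2 |

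So the claim in 6.3.2 to cover all PRO endpoints does not match its own subsections, since HLIQ and PGIC-H are not t-tested there.

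SAP 6.2.8.1 tests 10 domains and the total score. Leaving out Physical Health, 10 − 1 = 9 domains plus the total score, or 10 Haem-A-QoL scores, lie outside Table 2. Neither its footnote nor its improvement criterion protects them.

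**Illustration**

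Inputs: n = 40 (SAP 5, primary analysis), df = 40 − 1 = 39, alpha 0.05 (SAP 5.1). Assumed: a true standardised improvement d (mean change divided by the SD of the change) of 0.2 to 0.8, coded as negative for Haem-A-QoL.

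The paired t statistic follows a noncentral t distribution with 39 df and noncentrality −d√40. For d = 0.5 this is −0.5 × 6.325 = −3.16.

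- Literal reading: reject if t exceeds the upper 5% point of t on 39 df.
- Two-sided rule of SAP 5.1: count significance in the improving direction, that is, t below the lower 2.5% point.

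| Assumed d | Improvement found significant, literal rule (one-sided 0.05) | Improvement found significant, two-sided 0.05 |
|---|---|---|
| 0.2 | 0.0019 | 0.23 |
| 0.3 | 0.0002 | 0.46 |
| 0.5 | below 0.00001 | 0.87 |
| 0.8 | below 0.00001 | 0.998 |

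For a single result: an observed t of −3 on 39 df gives p = 0.998 against the alternative of a positive difference, and two-sided p = 0.005.

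The two rules therefore give very different answers on Haem-A-QoL, and what matters is which one governs each score. For Physical Health, Table 2 names the endpoint, requires improvement, and is footnoted as two-sided; 6.2.8.1 adds no direction. For the other ten Haem-A-QoL scores, only the general default in SAP 5.1 stands against 6.3.2.

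**The case against.** The strongest reply is that 6.3.2 does not govern the gatekept test. It sits under Other Endpoints, while Haem-A-QoL Physical Health is a secondary endpoint with its own section and its own line in Table 2. The SAP writes one-sided where it means it, as for FIX:C, and 6.3.2 never uses the term. Protocol 9.4.1 gives the aim of the PRO comparison as assessing improvement from baseline. SAP 6.2.8.1 also requires the change from baseline with 95% limits, so a wrong sign would be visible.

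Most of this stands. A reader might infer that a true improvement in Physical Health would fail step 8 and halt the sequence, or that a true worsening would be declared a success. The documents do not support either: the Table 2 criterion and footnote are specific to that test and point the other way. The t of −3 and the values of d above are illustrations, not expected results. HLIQ adds almost nothing, because no t-test of it is described in its own subsection.

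What the reply does not remove is the sentence itself. It says all PRO endpoints, it is wrong for Haem-A-QoL on the natural reading, and no order of subtraction rescues it. Table 2 also leaves the improving sign to be inferred from the scale descriptions in SAP 3.2.8.

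**Conclusion.** The point holds as a minor inconsistency. SAP 6.3.2 states a directional rule that is wrong for Haem-A-QoL if the difference is post minus baseline, wrong for HAL if it is the reverse, and at odds with SAP 5.1 either way.

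The direct exposure is the nine other Haem-A-QoL domains and the total score, all outside the gatekeeping sequence. For Physical Health the loss is conditional: only if 6.3.2 were programmed over Table 2, its footnote and 6.2.8.1 would step 8 fail, taking steps 9 and 10 with it. Steps 1 to 7, which include the primary endpoint, the key secondary endpoints and both ABR superiority tests, come earlier and are unaffected in any case.

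This rests on reading the difference as post minus baseline, which is natural but not stated. The probabilities in the working depend on the assumed d and on 40 complete pairs.

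**What to change.** In SAP 6.3.2, replace the directional phrase with a two-sided paired t-test of mean change (post minus baseline) equal to zero. State that improvement is a negative change for Haem-A-QoL and a positive change for HAL and the EQ-5D-5L VAS, and have the sponsor confirm the direction of the EQ-5D-5L index. Limit the sentence to the PROs that are actually t-tested, which leaves out HLIQ and PGIC-H.

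Optionally, add a note to Table 2 that steps 8 and 9 pass only with two-sided p < 0.05 and the improving sign: mean change below zero for Haem-A-QoL Physical Health, above zero for the HAL component.

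The cost is one sentence and, if wanted, one footnote. No data collection, sample size or alpha allocation changes. It is best done before database lock, because choosing between the two passages after open-label data have been seen would look post hoc.
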